## **SECTION B: RESEARCH METHODOLOGY**

### **B1. ABSTRACT**

Short-term negative energy balance (i.e., energy deficit) downregulates muscle protein synthesis and upregulates whole-body proteolysis and amino acid (AA) oxidation, thereby increasing nitrogen excretion and exacerbating whole-body and skeletal muscle protein loss. Consumption of quality proteins high in essential amino acid (EAA, i.e., the active anabolic component of protein) content may attenuate protein loss during energy deficit by restoring whole-body and skeletal muscle anabolic potential to that observed in a eucaloric state. During energy balance, muscle protein synthesis appears to be maximally stimulated after consuming 15 g of EAA at rest and after conventional resistance-type exercise. In response to a short-term energy deficit that downregulated basal muscle protein synthesis by as much as 27%, consuming 15 g (~7.5 g EAA) and 30 g (~15 g EAA) of whey protein after a bout of resistance exercise restored muscle protein synthesis rates to resting, fasted rates observed in the eucaloric state in a dose dependent manner. The effect of EAA intakes above 15 g on resting and post-exercise muscle protein synthesis and the whole-body protein anabolic response during acute energy deficit has not been determined. To address this, we will assess resting and post-resistance exercise whole-body and skeletal muscle protein synthesis responses to across a spectrum of EAA intakes following a well-controlled, short-term (5-d) energy deficit (30% energy deficit). Using a randomized, double-blind, cross-over design, 20 resistance trained ( $\geq 2$  d/wk for the past 6 mo) adults will undergo two, non-consecutive 5-d energy deficit periods, separated by a 14-d washout period. Resting and post-resistance exercise (single leg exercise model) whole-body protein turnover and skeletal muscle protein synthesis responses to two different doses of EAA (standard, 0.10 g/kg vs high, 0.30 g/kg) will be determined the morning after completing the 5-d energy deficit. This design will test the hypothesis that higher absolute doses of EAA are required to maintain resting and post-exercise anabolic responses during energy deficit. Risks include those associated with venous catheterization, muscle biopsies, DEXA, exercise, and the discomfort of moderate underfeeding.

[figure not shown]
### **B2. BACKGROUND AND SIGNIFICANCE**

Periods of negative protein balance (i.e., breakdown > synthesis) are largely unavoidable during strenuous military operations, and is exacerbated by sub-optimal dietary protein and energy intake [1, 2]. Prolonged

[figure not shown]
negative protein balance and associated muscle loss resulting from reductions in muscle protein synthesis, and concomitant increases in whole-body proteolysis and amino acid oxidation, may compromise Warfighter performance and readiness [2, 3]. As such, studies that identify effective nutritional interventions that mitigate protein loss and sustain Warfighter health and performance during real-world operations are warranted.

### Understanding Anabolism and its Quantification at the Whole-Body Protein Level

Anabolism is essentially the balance between protein synthesis and protein breakdown, which change in magnitude in response to various stimuli and stressors (e.g., EAA, exercise, hormones, stress, etc.). The application of stable isotope methodology allows for the measurement of these processes. In particular, quantifying labeled amino acid incorporation into intact proteins over time provides a measurement of fractional synthesis rate (FSR) of a given protein. In this regard, determining muscle FSR has become the most heavily relied upon method to evaluate the effects of various factors on muscle protein status. Conversely, assessing muscle fractional breakdown rate (FBR) is technically difficult, and the methods do not accurately account for a large bolus of EAA/protein intake over time [13-15]. As a result, muscle net protein balance is rarely measured, particularly in response to feeding. Instead, conclusions relevant to protein intake are based solely upon measurement of muscle FSR and the assumption that FSR is primarily responsible for changes in net protein balance in healthy young adults. As previously discussed, muscle FSR assessments alone have led to changes in sports nutrition recommendations regarding protein for muscle recovery, with no apparent consideration of net protein balance (i.e., anabolism). The potential contribution of protein breakdown (FBR) on net protein balance responses to increasing doses of EAA, particularly during negative energy balance, has never been studied.

While there is limited quality data on FBR, especially in response to feeding, the quantification of net protein balance at the whole-body level provides valuable additional insight on overall protein status, especially when combined with muscle FSR measures. In a recent study, postprandial muscle FSR and whole-body protein turnover were determined at rest and in response to resistance exercise to evaluate the overall body protein response to consuming mixed-meals with either 40 g or 70 g of high-quality protein [16]. As expected, muscle FSR was not different between protein intakes (**Figure 3**), indicating a similar, and probably maximal muscle protein synthetic response to each protein dose. However, whole-body net protein balance was significantly higher after consuming 70 g versus 40 g; an effect largely attributed to a dramatic decrease in whole-body protein breakdown (**Figure 4**).

**Figure 3.** Muscle protein synthesis in response to a mixed-nutrient meal with 40 g or 70 g of quality protein intake in young men and women.

**Figure 4.** Whole-body protein kinetics in response to a mixed-nutrient meal with 40 g or 70 g of quality intake in young men and women. NB - net protein balance; PS – protein synthesis; PB – protein breakdown. \* $p < 0.05$ ; \*\*\* $p < 0.0001$ .

These results point to a responsible metabolic mechanism that would **not** be evident if muscle protein synthesis was the only kinetic outcome studied. These results suggest that the abundance of circulating amino acids from exogenous sources reduces the reliance upon muscle protein breakdown to provide the amino acid precursors to sustain protein synthesis. Therefore, protein synthesis is maintained at a level commensurate with tissue intracellular concentrations. These data also indicate that relying upon only muscle FSR measures in response to protein intake may underestimate the total body anabolic response, which from a nutritional standpoint, reflects the total gain of body protein, and in more stressful circumstances (i.e., military operational stress), body protein health/status over time [17].

#### Intracellular Amino Acid Availability and Whole-Body Protein Anabolism

There appears to be a direct linear relationship between the rate of appearance of AA into the muscle intracellular pool (via inward AA transport and AA release from protein breakdown) and the rate of muscle protein synthesis [18, 19]. This finding indicates, in part, that increases in circulating AA concentrations are directly related to increases in protein synthesis. The controlling factor for synthesis appears to be the intracellular concentrations of AA, which remain relatively constant with modest increases in plasma AA [19]. Once the maximum rate of synthesis is reached, intracellular concentrations rise in relation to the continued increase in plasma AA [19]. However, the point at which intracellular AA increase does not necessarily coincide with the maximal *anabolic* response. Though protein synthesis may reach a maximum, net anabolism may continue if the rise in intracellular concentrations signal a reduction in the rate of protein breakdown [20]. Thus, even with a maximal synthetic response, further anabolism is achievable through a decrease in protein breakdown. Net anabolism is then dictated by the magnitude of decrease in protein breakdown. In this regard, the relationship between AA availability and net anabolism is linear, with no discernable plateau at higher levels of protein intake. This aspect of protein kinetics in response to EAA/protein intake is only evident when

both synthesis and breakdown are measured at the whole-body level. Preliminary work is consistent with this relationship, and demonstrates that whole-body net protein balance increases linearly with protein intake (**Figure 5**) [16]. This kinetic insight provides an integrated picture of whole-body protein status. Further, though

[figure not shown]

Figure 5. Relationship of protein intake in mixed meal and whole-body net protein balance.

not a direct measure of skeletal muscle protein turnover, changes in whole-body net protein balance are consistent with measures in muscle, due to the large contribution (by mass) of skeletal muscle to whole-body protein turnover. We suggest that assessing whole-body net protein balance may be of greater importance than measures in muscle that respond to the increasing stress of strenuous military operations, as it reflects the protein turnover status of many tissues that are less prominent in a non-stressed state. However, no studies have thoroughly examined the relationship between skeletal muscle and whole-body protein anabolism in response to various amounts of EAA during stress.

### Molecular Regulation of Skeletal Muscle Anabolism

Muscle protein synthesis rates (i.e., muscle FSR) are governed by the mechanistic target of rapamycin complex 1 (mTORC1) [21, 22]. The mTORC1 pathway can be influenced by exercise, energy balance, and EAA availability [23]. Resistance exercise and increased intracellular EAA concentrations can independently and synergistically activate mTORC1, resulting in a transient upregulation of anabolic signaling, mRNA translation initiation, elongation, and, ultimately, FSR [24-26]. We demonstrated blunted mTORC1 activation and downstream signaling following endurance exercise and recovery protein ingestion (25 g whey protein isolate) during a sustained energy deficit (unpublished data), yet whether consuming EAA in amounts greater than that present in 25 g of whey protein (~12.5g EAA) can overcome the apparent anabolic resistance during energy deficit has not been studied.

MicroRNA may be a potential mechanism governing adaptive mTORC1 signaling responses to anabolic stimulation [27]. Skeletal muscle-specific microRNA expression, myomiR; miR-1, miR-133a, miR-133b, miR-206, miR-208, miR-221, miR-222, miR-486, miR-499 [28], can be altered by acute anabolic stimulation [27, 29-31]. After resistance exercise, miR-1, miR-133a, miR-133b, and miR-206 expression are downregulated [29, 32]. After endurance exercise, there is an upregulation or no change in expression of these miRNA [32-34]. However, when endurance exercise is combined with EAA ingestion, myomiR expression is downregulated or unchanged immediately post-exercise and during recovery. Divergent myomiR expression responses to various exercise modes, with or without EAA intake, may be sensitive to muscle protein synthesis rates, as miR-206 and miR-499 expression were recently shown to be inversely associated with muscle FSR during exercise [32]. MyomiR target and inhibit molecular markers within the mTORC1 pathway. As such, downregulation in their expression may enhance anabolic signaling. However, while these data suggest that myomiR expression is modulated in response to both exercise and EAA, this relationship has never been studied in the context of short-term energy deficit.

### **B3. MILITARY RELEVANCE**

The use of a combat ration item designed to provide optimal protein quality and quantity to promote recovery from significant operational stress may increase combat effectiveness by sparing skeletal muscle and whole-body protein. Efforts to develop an optimized protein-containing food product would be consistent with recommendations from several internationally recognized organizations, and a recent consensus document developed specifically for military operations [10-12]. A consistent recommendation among these entities is the consumption of high-quality protein-containing products during periods of substantial metabolic stress, particularly during situations that elicit a negative energy and protein balance. This proposal will provide the initial evidence to support the production of a recovery-based food component for combat rations. It will define the metabolic responses of various EAA quantities. Future efforts will extend upon the present study's evidence and assess protein quality and the accompanying food matrix to support skeletal muscle and whole-body protein sustainment and/or recovery from military operational stresses. The proposed studies support the

joint effort between USARIEM and the US Army Combat Feeding Directorate, i.e., the Army Science and Technology Objective: Nutritionally Optimized Food Products for an Expeditionary Force (R.MRMC.2017.01).

#### **B4. OBJECTIVES/SPECIFIC AIMS/RESEARCH QUESTIONS**

##### **Objectives**

1. Characterize effects of essential amino acid (EAA) quantity on resting and post-resistance exercise muscle and whole-body protein kinetic responses during short-term energy deficit.
2. Determine the effects of essential amino acid (EAA) quantity on resting and post-resistance exercise skeletal muscle anabolic signaling during short-term energy deficit.

##### **Hypotheses**

1. Resting and post-resistance exercise muscle protein synthesis will be stimulated to a greater degree with higher (0.30 g/kg) versus lower (0.10 g/kg) EAA intake during acute, moderate energy deficit.
2. Resting and post-resistance exercise whole-body protein balance will be greater with higher (0.30 g/kg) versus lower (0.10 g/kg) EAA intake during acute, moderate energy deficit.
3. Resting and post-resistance exercise whole-body protein balance will be more positive with higher (0.30 g/kg) versus lower (0.10 g/kg) EAA intake during acute, moderate energy deficit due to a greater increase in whole-body protein synthesis.
4. Resting and post-resistance exercise skeletal muscle anabolic signaling will be stimulated to a greater degree with higher (0.30 g/kg) versus lower (0.10 g/kg) EAA intake during acute, moderate energy deficit.

#### **B5. RESEARCH PLAN**

##### **B5.1 Research Design**

This study will be a randomized, double-blind, cross-over controlled trial. Before the study begins, a research team member ([name]) will generate the randomization scheme using a random number generator (<http://randomization.com>). [name] will be responsible for preparing and coding the individualized EAA drinks for each trial and she will hold the randomization code until the study has been completed (i.e., data collected and analyzed). The study investigators will be blinded to this process. The code will be broken by [name] after the primary outcomes (i.e., muscle protein synthesis and whole-body protein balance) have been statistically analyzed by the study investigators (i.e., [name], [name], [name], [name], [name], and [name]).

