### Western Blotting

Approximately 30 mg of muscle will be homogenized in ice-cold buffer (1:10 wt/vol) containing 50 mM Tris-HCl (pH 7.5), 5 mM Na-pyrophosphate, 50 mM NaF, 1 mM EDTA, 1 mM EGTA, 10% glycerol (v/v), 1% Triton-X, 1 mM DTT, 1 mM benz-amidine, 1 mM PMSF, 10  $\mu$ g mL trypsin inhibitor and 2  $\mu$ g mL aprotinin. Homogenate will be centrifuged for 15 min at 10,000  $\times$  g at 4°C. Protein concentration of supernatant (lysate) will be determined using 660 nm Protein Assay (ThermoFisher Scientific, Waltham, MA, USA or equivalent). Phosphorylation status and total protein expression of molecular markers associated with anabolism will be determined using Western blotting techniques. Muscle lysates will be solubilized in Laemmli buffer, with equal amounts of total protein (15  $\mu$ g) separated by SDS-PAGE using precast Tris-HCl gels (Bio-Rad). Proteins will be transferred to polyvinylidene fluoride (PVDF) membranes and exposed to commercially available primary antibodies of intracellular markers involved with skeletal muscle anabolism and proteolysis to include but not limited to Akt, p-AktSer473, mTOR, p- mTORThr2448, p70S6K, p-p70S6KThr424, rpS6, and rpS6Ser235/236 (Cell Signaling Technology, Danvers, MA, USA or equivalent) at 4°C overnight. Labeling will be performed using secondary antibody (anti-rabbit IgG conjugate with horseradish peroxidase; Cell Signaling Technology), and chemiluminescent reagent will be applied (Super Signal, West Pico Kit; Pierce Biotechnology, Rockford, IL, USA). Blots will be quantified using a phosphoimager (ChemiDoc XRS; Bio-Rad) and Image Lab software (Bio-Rad) or similar models. To confirm equal protein loading per well a normalizing protein such as GAPDH or HSP90 will be assessed.

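### Section B5.1 gives two different points for breaking the randomization code; the second allows the signalling outcomes of Hypothesis 4 to be quantified or analysed with the dose known

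*Combined protocol and SAP*

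**What the plan says.** B5.1 (Research Design) describes a randomized, double-blind cross-over trial. The team member who prepares and codes the drinks is to "hold the randomization code until the study has been completed (i.e., data collected and analyzed"). The next sentence says: "The study investigators will be blinded to this process". The sentence after that has the same person break the code "after the primary outcomes (i.e., muscle protein synthesis and whole-body protein balance) have been statistically analyzed by the study investigators".

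B4 makes signalling one of the trial's two objectives: "Determine the effects of essential amino acid (EAA) quantity on resting and post-resistance exercise skeletal muscle anabolic signaling during short-term energy deficit". It also gives signalling its own directional hypothesis, Hypothesis 4, which begins "Resting and post-resistance exercise skeletal muscle anabolic signaling will be stimulated to a greater degree" and compares 0.30 g/kg with 0.10 g/kg.

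The signalling methods are in B5.4, under mRNA and microRNA Expression and under Western Blotting. Both sections name core targets and leave the lists open to additions. For the blots, "a normalizing protein such as GAPDH or HSP90 will be assessed" as a check on equal loading. Neither section says who quantifies the blots or the PCR, whether that person is masked to dose, or whether the work comes before or after the code is broken.

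**The concern.** A double-blind trial needs a single, unambiguous event that ends the blind. Here there are two, and the more specific one is tied to two outcomes that leave out half of the stated objectives. If it is followed as written, the laboratory and analysis work for Objective 2 could be done by people who know which of each volunteer's two trials was the high dose.

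This matters more for signalling than it would for a tightly specified endpoint. The protein, mRNA and microRNA targets can be extended, and the loading protein is given by example. B5.4 refers to the statistical section for the fold-change method, but B5.8.2 does not describe it. The ANOVA in B5.8.2 names only muscle FSR and whole-body protein turnover. With so little fixed in advance, masking is one of the few safeguards left for a directional hypothesis. A dose effect found after the code was open would be harder to defend as a blinded result.

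**Working it through.** The plan gives no figure on this point and no arithmetic applies. The check sets the release rules beside the outcomes they have to protect.

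**Step 1. The two rules in B5.1.**

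| | Event that releases the code | Covers muscle FSR and whole-body balance? | Covers signalling? |
|---|---|---|---|
| Rule 1 | Study complete: data collected and analysed, with no restriction by outcome | Yes | Yes, read literally |
| Rule 2 | The two named primary outcomes have been statistically analysed | Yes | No |

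**Step 2. When do the rules agree?** There are two ways.

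- *Analysed in rule 1 means the primary outcomes only.* The inconsistency then disappears, but signalling is protected by neither rule.
- *All signalling work is finished before the primary analysis.* The rules then agree in practice and signalling is protected, but no section states that order.

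If neither holds, the rules conflict, and rule 2 allows the earlier release.

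**Step 3. Does another section close the gap?**

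- *B5.4, Western Blotting and mRNA and microRNA Expression:* nothing on masked quantification or on timing relative to the code break.
- *B5.4 (stable isotope analysis), B5.5 and C5:* samples carry coded subject identification numbers. This is described as protection of identity, not as masking of dose.
- *B5.8.2:* the dose comparison named is for FSR and whole-body turnover. Signalling, and when it is analysed, is not mentioned.

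No section closes it.

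**Step 4. What opening the code reveals.** Each volunteer receives both doses, so the code amounts to the order of doses for each volunteer. Once opened, it identifies the dose for every sample from both of that volunteer's trials, including samples kept for signalling. Releasing it for one outcome therefore leaves the others masked only if the people working on them are kept from it.

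**Step 5. Extent.** Objectives exposed: 1 of 2 (Objective 2). Hypotheses exposed: 1 of 4 (Hypothesis 4). Primary outcomes exposed by this wording: 0 of 2, since both rules come after their analysis.

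**The case against.** The strongest reply is that the second sentence specifies the first: B5.1 states a general principle and then names the analyses that count. On that reading there is no contradiction, only loose drafting. This is a fair reading, and it is why the two statements are better called inconsistent than irreconcilable. It does not help signalling, which is then outside the only operative rule.

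A second reply is that opening the code after the primary analysis, while secondary laboratory work continues, is a legitimate design choice. The powered outcomes are safe, and dosing and volunteer blinding are untouched. That stands as far as the primary outcomes go. But signalling is a stated objective with its own directional hypothesis, and the text does not say that it is meant to be assessed open-label.

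A third reply is that the analyst has less freedom than it may seem. Equal amounts of total protein are loaded on the gels, GAPDH or HSP90 is there to confirm loading, core targets are named, and serum microRNA is normalised to the geometric mean of a spike-in and internal controls. This also stands in part. Much of the remaining openness is a matter of pre-specification, which a sealed code does not cure by itself.

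A reader might go further and infer that the primary results will be ready first because the isotope samples go to an outside laboratory. The documents do not support that. They give no assay order, and off-site analysis could equally be the slower part.

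**Conclusion.** The point holds as an inconsistency to be reconciled, with a real but limited consequence. B5.1 states two release points; under the second, the code may be broken before the outcomes for Objective 2 and Hypothesis 4 are quantified or analysed, and no section requires that work to be masked. The primary outcomes are not affected.

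Two stronger readings are tempting. One is that the trial plans to quantify signalling unblinded; the text permits this but does not say so, and the blots and PCR could be completed before the code is opened. The other is that a definite inflation of the false-positive rate can be attached to the wording. It cannot: choosing among targets or normalisers after seeing results inflates error whether or not the dose is known, so such a figure would measure missing pre-specification, not the effect of unblinding.

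The conclusion assumes that the second sentence of the pair would be acted on as written and that no unpublished laboratory procedure already requires masked quantification. If one does, the remedy is to cite it. The change is worth making because it is cheap.

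**What to change.** State one release point in B5.1. Either of two forms would do:

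1. The code stays sealed until blot and PCR quantification, normaliser choice and sample exclusions are locked, and the dose comparisons for all four hypotheses have been run and locked.
2. If primary results are needed sooner, the code is released for the primary data set only, and everyone who quantifies or analyses signalling stays masked until the signalling data and dose comparisons are locked. The protocol should then say, by role, who has access.

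In either form, add a sentence to the two signalling assay sections of B5.4 that quantification is done without knowledge of dose. Locking the normaliser and exclusions before the comparison also deals with part of the selection problem that masking alone leaves.

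The cost is protocol wording. Under the first form, unblinded primary results may wait for the signalling work; under the second, the laboratory analysts stay masked longer and access to the code has to be controlled by person. Sample size, visits and assays do not change.
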